6.5 The end of study

6.5.1. Definition of the end of the study

Previous talimogene laherparepvec single agent study showed that the median time to response was 4.1 months, and 50 % of these responders had progressive disease (PD) (defined by modified WHO criteria) prior to response. In this study talimogene laherparepvec administration will continue for at least 10 cycles (approximately 5 months) unless uncontrolled disease progression is observed. Beyond 10 cycles, progressive disease will be measured based on RECIST ver1.1.

6.5.2. Uncontrolled disease progression

Uncontrolled disease progression is defined as rapid growth of multiple measurable or non-measurable new lesions, or sum of the longest diameter of existing targeted lesions is >40% from the baseline.

Immunotherapeutic agents such as talimogene laherparepvec may produce antitumor effects by potentiating endogenous cancer-specific immune responses. The response patterns seen with such an approach may extend beyond the typical time course of responses seen with cytotoxic agents, and can manifest a clinical response after an initial increase in tumor burden or even the appearance of new lesions

7.0. Pretreatment evaluation (within 6 weeks prior to study enrollment)

7.1. Informed consent/ patient registration

The study will be discussed with the patient, and any patient wishing to participate must give informed consent prior to any study-related procedures or change in treatment. A signed, Institutional Review Board approved, informed consent form must be obtained from patients before any study specific procedures or registration for study treatment can occur. All patients will be registered in the Clinical Oncology Research system.

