- Known leukemia or lymphoma
- Primary immunodeficiency state such as Severe Combined Immunodeficiency Disease.
- Concurrent opportunistic infection.
- Receiving systemic immunosuppressive therapy (> 2 weeks) including oral steroid doses > 10 mg/day of prednisone or equivalent within 7 days prior to the initiation of study treatment.
- Known hepatitis B or C infection
- Congenital or acquired cellular and/or humoral immune deficiency.
- Other signs or symptoms of immune system suppression

5.2.11. Active herpetic skin lesions or prior complication of HSV-1 infections (e.g. herpetic encephalitis or keratitis).

5.2.12. Currently pregnant or breast-feeding, or planning to become pregnant during study treatment and through 3 months after the last dose of study treatment.

5.2.13. Female subject of childbearing potential who is unwilling to use acceptable method(s) of effective contraception during study treatment and through 3 months after the last dose of talimogene laherparepvec. (Women of not childbearing potential: post-menopausal [age > 55 years with cessation of menses > 12 months or < 55 years but not spontaneous menses for at least 2 years or < 55 years and spontaneous menses within the past 1 year, but currently amenorrheic (eg, spontaneous or secondary to hysterectomy), and with postmenopausal gonadotropin levels (luteinizing hormone and follicle-stimulating hormone levels > 40 IU/L) or postmenopausal estradiol levels (< 5 ng/dL) or according to the definition of "postmenopausal

range" for the laboratory involved] or who have had a hysterectomy, bilateral salpingectomy, or bilateral oophorectomy).

5.2.14 Sexually active subjects and their partners unwilling to use male or female latex condom to avoid potential viral transmission during sexual contact while on treatment and within 3 months after treatment with talimogene laherparepvec.

5.2.15. Currently enrolled in another clinical trial for investigational drugs, procedures or device (excluding non-cancer treatment trials) or receipt of an investigational agent or device within 4 weeks of the initiation of study treatment

5.2.16. Intermittent or chronic treatment with antiherpetic drugs, except for topical agents.

5.2.17. Patients who is known sensitive to any of the products or components to be administered during treatment with talimogene laherparepvec.

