5.2.18. Chronic oral or systemic steroid medication use at a dose of >10 mg/d of prednisone or equivalent [steroids with low systemic absorption (e.g. triamcinolone hexacetonide) injected into joint space are allowed]

5.2.19. Prior therapy with tumor vaccine, or received live vaccine within 28 days prior to the initiation of study treatment.

5.2.20 Subjects who are unwilling to minimize exposure with his/her blood or other body fluids to individuals who are at higher risks for HSV-1 induced complications such as immunosuppressed individuals, individuals known to have HIV infection, pregnant women, or infants under the age of 3 months, during talimogene laherparepvec treatment and through 30 days after the last dose of talimogene laherparepvec.

5.2.21 Prior immunosuppressive, chemotherapy, radiotherapy (in which the field encompassed a planned injection site), biological cancer therapy (monoclonal antibodies), or major surgery within 28 days prior to enrollment or has not recovered to CTCAE grade 1 or better from adverse event due to cancer therapy administered more than 28 days prior to enrollment.

5.2.22 Prior radiotherapy in which the field does not overlap the injection sites or non-immunosuppressive targeted therapy within 14 days prior to enrollment or has not recovered to CTCAE grade 1 or better from adverse event due to cancer therapy administered more than 14 days prior to enrollment

5.2.23 Patients who have extensive skin disease, defined as total area of skin involvement/lesions that comprise $\geq 10\%$ of body surface area. Refer to "Rule of Nines" in Appendix 15.6 that will be the guide for specific percentages per body part(s). Skin involvement comprising $\geq 5\%$ to upper anterior chest wall or $\geq 5\%$ to upper posterior back is excluded.

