7.2.12. Breast sonography with axillary assessment if clinically indicated

7.2.13. Ultrasound-guided core biopsy of local recurrence if samples (i.e., paraffin block or 5-10 unstained slides from the local recurrence) are not available. The imaging physician will perform the biopsy if indicated at MD Anderson.

7.2.14. HSV serology: serum HSV type 1 IgG.

7.2.15. Systemic immunity in serum or plasma levels of, IL-2, IL-12, TNF-alpha (α), IFN- alpha (α); and phenotype for T-cell subsets (CD3, CD4, CD8, CD25), and natural killer-cell subsets (CD16, CD56) will be determined via multiparameter fluorescence activated cell sorting (FACS) analysis (percentage and absolute numbers) in [name] laboratory at MD Anderson.

7.2.16. Photography of the local recurrence in the chest wall.

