8.3 Study Calendar

Evaluation and treatment	Screening	Cycle 1 Day 1	Cycle 2 (D22+/-5 days)	Cycle 5 (D64 +/- 5 days)	Cycle 7 and every 2 cycles	Follow up⁹
Time	Baseline (within 6 weeks)	Prior to talimogene laherparepvec injection				
Eligibility, screening, consent, and registration	X					Patients will be monitored for 1 year after removal from the study or until death, whichever occurs first.
Medical history	X					
Staging with tumor measurements	X					
Photography of chest wall	X ¹		X	X	X	
Biopsy of local recurrence [HE, IHC]	X ⁸			X ⁸		
Biopsy of easily accessible distant metastasis [HE, IHC]				X ⁸		
Correlative immune study	X			X ⁷		
Physical examinations, vital signs	X	X ²	X	X	X	
ECOG PS	X	X ²	X	X	X	
Hematology assessment and Biochemical profiles ^{3,5}	X	X ²	X	X	X	
Tumor markers (CA27.29) ¹¹ , IgG (baseline only)	X			X	X ¹¹	
Chest X-ray; Breast sonography ¹³	X					
Pregnancy test if applicable ¹⁰	X					
PET-CT or CT scan of bone/abdomen/chest as clinically indicated	X			X	X ⁴	
Disease assessment ¹²				X	X	

Adverse events ⁵	X	X	X	X	X	
Talimogene Laherparepvec injection ⁶		X	X	X	X	

1. Within 1 week prior to treatment
2. No need to repeat if within 7 days from baseline
3. Hematology include CBC, differential count and platelet count; and biochemical profiles SMA include Na, K, BUN, creatinine, Mg, calcium, AST, ALT, LDH, total bilirubin
4. Repeat every 4 cycles as clinical indicated
5. Before each cycle. Reporting exposure to talimogene laherparepvec and should be collected for the duration of the study and safety f/u
6. Starting cycle 2, Talimogene Laherparepvec injection will be given every 2 weeks until disease progression
7. Correlative immune study will be repeated before cycle 5 and at the end of study if available.
8. Core biopsy of local recurrence at baseline if samples (i.e., paraffin block or 5-10 unstained slides) from the local recurrence are not available. Core biopsy of either distant metastasis or local recurrent lesions before cycle 5 based on patient status.
9. a. Safety Follow-Up: should be conducted approximately 30 days after the last dose of trial treatment or before the initiation of a new anti-cancer treatment, whichever comes first. Safety Follow-Up Visit can be done in the clinic, or by phone if patient is not willing to come to the clinic for follow up.
- b. Unexpected AEs: Patients removed from study for unexpected adverse events will be monitored until AE is resolved or stabilized.

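### The baseline immune sample can precede the 28- and 14-day washouts, so in patients who recently stopped prior therapy the change to cycle 5 can mix recovery with drug effect

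*Combined protocol and SAP*

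**What the plan says.** Section 7.0 is headed "Pretreatment evaluation (within 6 weeks prior to study enrollment". Among its items is 7.2.15, which covers "Systemic immunity in serum or plasma levels of, IL-2, IL-12, TNF-alpha" and IFN-alpha, together with "phenotype for T-cell subsets (CD3, CD4, CD8, CD25), and natural killer-cell subsets (CD16, CD56) will be determined via multiparameter fluorescence activated cell sorting". That item carries no time limit of its own.

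The study calendar (8.3) labels the screening column "Baseline (within 6 weeks" and marks the correlative immune study at Screening and at Cycle 5, with no entry at Cycle 1 Day 1. Its footnote 7 adds: "Correlative immune study will be repeated before cycle 5 and at the end of study if available".

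The washouts are set separately. Section 5.2.21 excludes prior immunosuppressive therapy, chemotherapy, radiotherapy over a planned injection site, "biological cancer therapy (monoclonal antibodies), or major surgery within 28 days prior to enrollment". Section 5.2.22 excludes radiotherapy away from the injection sites and non-immunosuppressive "targeted therapy within 14 days prior to enrollment".

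Section 1.3 makes change in these markers a correlative objective. Section 13.1 plans to relate marker change to response status and to model it over time with mixed effects.

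**The concern.** A baseline is meant to show the patient's immune state just before the first injection. Here it can be drawn while an earlier regimen is still being given, or soon after it stops. Section 7.1 requires consent before any change in treatment, so screening during prior therapy is foreseeable.

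If that therapy had lowered T- or NK-cell numbers or shifted cytokines, part of the movement by cycle 5 would be recovery. The trial has one arm, so no control group shows how much. The plan states no adjustment for time since prior therapy, and concomitant medications are kept out of the case report form (12.1) and the final analysis (7.2.2).

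The protocol's account of the phase 1 study (4.4.3) shows what is at stake. T-cell findings in those biopsies could not be attributed to treatment because there were no baseline data. A baseline drawn on or just after other therapy risks a similarly inconclusive reading of the blood markers.

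**Working it through.** **Plan's own figures.** The plan gives no figure on this point. Its two-stage operating characteristics (13.1) reproduce by exact binomial calculation with 13 then 22 patients, stopping at 0/13 and rejecting at 3/35 or fewer:
- At 5%: early stop 0.513, promising 0.0844, expected size 23.71 (stated 51%, 8.4%, 23.7).
- At 20%: 0.055, 0.903, 33.79 (stated 5%, 90%, 33.8).

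No immune measurement enters these figures.

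**Inputs for the timing check.**
- Screening window: 6 weeks = 42 days before enrollment (7.0, 8.3).
- Washouts: 28 days (5.2.21) and 14 days (5.2.22), both counted back from enrollment.
- Second dose on day 22, then every 2 weeks (6.1); cycle 5 on day 64 +/- 5 (8.3).

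**Step 1: does anything tighten the window for this sample?** No.
- Calendar footnote 1 (1 week) is attached to photography.
- Footnote 2 (7 days) is attached to examination, performance status, and hematology and biochemistry.
- The 5-day tolerance in section 8.0 applies around a scheduled time, and for screening that time is the 6-week window itself.

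**Step 2: window against washouts.**
- 28-day washout: 42 - 28 = 14 window days before it starts (14/42 = 33%).
- 14-day washout: 42 - 14 = 28 window days before it starts (28/42 = 67%).

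A draw on those days can be taken while the therapy is still running; a later draw falls inside the washout. These are widths of the window, not shares of patients.

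**Step 3: length of the baseline-to-cycle-5 interval.** Assume enrollment and first dose fall on the same day. The documents state no maximum gap, and any gap adds pre-drug time.
- Cycle 5: 22 + 3 x 14 = day 64.
- Day 1 draw: 64 - 1 = 63 days (58 to 68 with the tolerance), all on study.
- Earliest permitted draw: 42 + 63 = 105 days (100 to 110), with 42/105 = 40% of it before any study drug (42/110 = 38% to 42/100 = 42%).

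**Step 4: illustrative size, on assumed inputs not in the documents.** Suppose a marker sits D standard deviations low on prior therapy, the last dose is at day -28, recovery is exponential with half-life h, and the drug has no effect. The spurious rise is D x (0.5^(t0/h) - 0.5^(t1/h)). Here t0 is days from last dose to the draw (0 if drawn on therapy) and t1 = 28 + 63 = 91. For D from 0.25 to 1.0 and h from 14 to 56 days:

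| Baseline draw | Spurious rise (SD) |
|---|---|
| Day -42 or -28 | 0.17 to 0.99 |
| Day -14 | 0.12 to 0.60 |
| Day 0 | 0.06 to 0.39 |

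For example, with D = 1.0 and h = 28, a draw at day -42 gives 1 - 0.5^(91/28) = 0.89, and a draw at day 0 gives 0.5 - 0.105 = 0.39. A later draw shrinks the artefact without removing it.

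**The case against.** The strongest reply accepts the scheduling gap and disputes its reach. Four stronger readings are tempting, and the documents do not support them.

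- **That most patients are affected.** Section 5.1.3 admits patients who failed at least one regimen, or who have stable disease for at least 2 months on capecitabine, hormonal or anti-HER-2 therapy. It gives no proportions, and having failed a regimen does not mean having just stopped one. Sections 6.3.3 and 8.0 let background therapy continue, and such patients may have no recovery phase.
- **That steroid exposure may run until a week before dosing.** Section 5.2.10 refers to more than 10 mg/day of "prednisone or equivalent within 7 days prior to the initiation of study treatment", which read alone would leave 42 - 7 = 35 window days exposed. But 5.2.18 excludes chronic use above 10 mg/day without a time limit, and 5.2.21 bars prior immunosuppressive therapy for 28 days. The point rests on the 28- and 14-day washouts alone.
- **That the comparison of responders with non-responders is biased.** A shift common to all patients largely cancels there. Bias needs draw timing or prior therapy to be related to response, which the documents do not show. Otherwise the effect is added noise.
- **That the trial's conclusions are at risk.** These markers are in neither the primary nor the secondary endpoints (13.2, 13.3).

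Two partial safeguards also exist. The blood count with differential is repeated at Cycle 1 Day 1 unless recent, so drift in total counts is partly visible, though not in subsets or cytokines. End dates of chemotherapy, targeted, radiation and hormone therapy are collected (12.1), so an adjustment is possible, although none is planned.

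All of this stands as a limit on scope. None of it places the sample after the washouts.

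**Conclusion.** The point holds in conditional form. The single pre-treatment immune sample can be drawn before the washouts start, and up to 42 days before any study drug even if dosing follows enrollment at once. For patients who stopped therapy shortly before enrollment, change to cycle 5 can then include recovery. The main casualty is the description of change over time.

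The timing follows directly from the text. The amount of bias does not: it depends on when patients are actually sampled, what they stopped and how fast they recover, and the documents give none of these. The standard-deviation figures are illustrative only. If every patient were sampled just before dosing, the extra pre-drug interval would vanish, although recovery after washout could continue. The point deserves correction because a missed pre-dose sample cannot be obtained later.

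**What to change.** **Patients enrolled from now on.** Amend 7.2.15 and the calendar so that the baseline immune sample is drawn at Cycle 1 Day 1 before the injection, or within the 7 days before it. Name that sample in 13.1 as the baseline for all change analyses.

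**Patients already treated.** Section 13.1 reports 8 treated when this text was written, and the new baseline cannot apply to them. Keep their screening sample, record its draw date, and use time from last prior therapy to that draw as a covariate or in a sensitivity analysis. Identify patients who never stopped background therapy separately, since that interval is undefined for them.

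**Cost.** An amendment to one item, one calendar cell and a sentence of the analysis plan, plus recording draw dates. The patient already attends the Day 1 visit, so no extra visit, tube or assay is needed. The drawbacks are two baseline timings within at most 36 patients, and some residual recovery after washout that a Day 1 draw does not remove.

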7.2. Pretreatment evaluation

7.2.1. Complete medical history and physical examination including breast examination, vital signs, height, weight, demographics, and adverse events.

7.2.2. We will document concurrent medications as a standard of care but not for protocol purposes. Concurrent medications will not be included in the final analysis. However, we will

document and report any unexpected severe toxicity that is deemed to be related to the concurrent medication.

7.2.3. Documentation of ECOG PS, menopausal status, and date of last menstrual period.

7.2.4. The breast will be carefully and clinically measured, and the location of the involved area will be described. Location and size of the tumor, axillary and supraclavicular node status, and clinical TNM stage will be recorded. Locally recurrent breast tumors and skin lesions should be recorded with medical photography. Measurements should be bi-dimensional and expressed in centimeters.

7.2.5. Complete blood count (CBC), differential count, and platelet count;

7.2.6. Chemical profiles- simultaneous multichannel autoanalyzer (SMA) (Na, K, blood urea nitrogen (BUN), creatinine, Mg, calcium, AST, ALT, LDH, total bilirubin)

7.2.7. If a female patient is of childbearing potential, a urine or blood pregnancy test should be performed no more than 3 days before the start of treatment.

7.2.8. Levels of tumor markers (e.g., cancer antigen CA 27.29) will be assessed.

7.2.9. Chest x-ray.

7.2.10. PET/CT or chest and abdominal CT scan if clinically indicated.

7.2.11. Bone scan only if PET/CT is not performed.

7.2.12. Breast sonography with axillary assessment if clinically indicated

7.2.13. Ultrasound-guided core biopsy of local recurrence if samples (i.e., paraffin block or 5-10 unstained slides from the local recurrence) are not available. The imaging physician will perform the biopsy if indicated at MD Anderson.

7.2.14. HSV serology: serum HSV type 1 IgG.

7.2.15. Systemic immunity in serum or plasma levels of, IL-2, IL-12, TNF-alpha (α), IFN- alpha (α); and phenotype for T-cell subsets (CD3, CD4, CD8, CD25), and natural killer-cell subsets (CD16, CD56) will be determined via multiparameter fluorescence activated cell sorting (FACS) analysis (percentage and absolute numbers) in [name] laboratory at MD Anderson.

7.2.16. Photography of the local recurrence in the chest wall.

8.0. Evaluation during study

The window for all assessments and treatments should be completed within 5 days of the scheduled time.

Patients will be allowed to continue current hormonal therapy, selected chemotherapy, targeted agents and/or anti-HER-2 therapy, which will be administered as standard of care, (per physician discretion) while receiving study drug.

8.1. Evaluation during talimogene laherparepvec:

- 8.1.1. Patients will have a CBC, differential count and platelet count before each cycle.
- 8.1.2. Patients may repeat the CBC, differential count and platelet count until recovery of these measures before the next cycle (absolute neutrophil counts \geq 1,000 and platelets \geq 100,000 per mm³).
- 8.1.3. Medical history and physical examination with vital signs, weight, and PS before cycles 2 and 5 and every additional 2 cycles of treatments.
- 8.1.4. Digital photography of chest lesions before cycles 2, 5, and every additional 2 cycles of treatment.
- 8.1.5. Toxic effects will be assessed before each cycle.
- 8.1.6. SMA (Na, K, BUN, creatinine, Mg, calcium, AST, ALT, glucose, LDH, and total bilirubin) will be performed before each cycle.
- 8.1.7. Levels of tumor markers (e.g., cancer antigen CA 27.29) will be assessed before cycle 5 and every additional 4 cycles of treatment.
- 8.1.8. Systemic immunity in serum or plasma levels of GM-CSF, IL-2, IL-12, TNF-alpha (α), IFN- alpha (α); and phenotype for T-cell subsets (CD3, CD4, CD8, CD25), and NK-cell subsets (CD16, CD56) will be determined via multiparameter FACS analysis (percentage and absolute numbers) before cycle 5 and at the end of study in [name] laboratory at MD Anderson.
- 8.1.9. PET-CT or CT of bone/ abdomen/chest should be performed before cycle 5 and before every additional 4 cycles of treatment as clinically indicated.
- 8.1.10. Disease assessment will be done at the end of cycle 4, cycle 8 and cycle 10.

8.2. Evaluation of distant metastases (before cycle 5)

If a patient has distant metastasis, every effort will be made to obtain tissues from an easily accessible metastatic site. If patient does not have distant metastasis or distant metastasis is not accessible, core biopsy of local lesions will be needed to collect tumor tissue. Every effort will be made to obtain biopsy tissue before cycle 5 for at least 60% of enrolled patients.

A pathologist collaborator will be notified before the biopsy and will handle the resected specimen. Every attempt will be made to identify any tumor change such as necrosis.

Hematoxylin and Eosin staining will be performed with formalin-fixed paraffin-embedded

blocks to determine tumor, and immunohistochemical (IHC) staining will be made for immunity assessment. IHC assays will include CD3, CD4, and CD8 for T-cell immunity assessment, CD20 for B-cell immunity assessment, and CD16, CD56, and Granzyme B for NK cell immunity assessment. Cleaved caspase 3 staining for an apoptosis assay, Ki67 for a proliferation assay, and HSV antigen staining will be performed. If the remaining sample is ample, CD45RO, TIA-1, FoxP3, CD25, OX-40, CD56, CD57, CD1a, CD208, myeloperoxidase, CD68, COX-2, MHC Class I, and MHC Class II will also be assessed in [name] laboratory at MD Anderson.

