5.1.9. Adequate hepatic function

- Aspartate aminotransferase (AST) $\leq 2.5 \times$ upper limit of normal (ULN) if liver metastases present
- Alanine aminotransferase (ALT) $\leq 2.5 \times$ ULN if liver metastases present
- Total bilirubin $\leq 1.5 \times$ ULN, OR direct bilirubin \leq ULN for a subject with total bilirubin level $> 1.5 \times$ ULN

5.1.10 Subjects must be candidate for intralesional injection into cutaneous, subcutaneous or nodal tumors with or without image ultrasound guidance defined as one or more of the following At least 1 injectable lesion $\geq 5 \text{ mm}$ in longest diameter, multiple injectable lesions that in aggregate have a longest diameter of $\geq 5 \text{ mm}$.

5.1.11. Female patients of childbearing potential must have a negative urine or serum pregnancy test no more than 3 days prior to starting study drug.

5.1.12. Patients must be able and willing to give written informed consent.

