6.0. Treatment plan

6.1 Talimogene laherparepvec injection

Talimogene laherparepvec will be given via intra-tumoral injection at visible locally recurrent breast cancer site and skin metastases if indicated at an initial dose of 10^6 PFU/mL for all sample size of 35. If patient has multiple lesions the lesion selection as the following:

- 1) If the largest lesion is > 5 cm, only this lesion will be used for injection;
- 2) If the largest lesion is < 5.0 cm, we will prioritize the size of the lesions (from large to small), and administer talimogene laherparepvec based on injection guideline in Table 3 below. The maximum dose of each course should not exceed 4.0 mL.
- 3) If patients do not have distant metastases, the lesion of lowest priority for injection should be left uninjected at least until it is biopsied.

The injection dose will not be affected by patients' actual body weight. The second talimogene laherparepvec dose will be administered 10^8 PFU/mL on day 22, and talimogene laherparepvec will be administered every 2 weeks after the second course with same dose with the maximum dose of 4.0 mL for each course (Figure 4). The injection dose varies according to the tumor spread area and using the talimogene laherparepvec injection volume guideline based on tumor size (Table 3). Distribution of the injection to separate sites will be permitted if the lesion is more than 5.0 cm diameter and/or multiple lesions. When disease diameter is greater than 5.0 cm and difficult to inject uniformly, we divide disease location tetrameric injection site with 1.0 mL administration each. On each treatment day, injections should be prioritized as follows:

[figure not shown]
- any new injectable tumor that has appeared since the previous injection
- by tumor size, beginning with the largest tumor and then the second largest tumor if agent available, otherwise treat in the following courses
- by tumor size, when similar size tumor exist, prioritize one and then the other tumor if agent available, otherwise treat in the following courses
- by tumor size, when huge tumor exist (greater than 10.0 cm), inject talimogene laherparepvec at different site for aiming uniform distribution in the following course.
- any previously uninjectable tumor(s) that is now injectable

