Within the guidelines of the algorithm in Table 3 and the prioritization model above, each lesion should be injected with the maximum amount possible at each visit before moving on to the next lesion, subject to tumor-specific limitations (such as the inability to inject the full amount into the lesion). Lesions should be injected until the maximum volume per day (4.0 mL) has been reached or there are no further injectable lesions, whichever comes first.

Lesion site preparation

- Talimogene laherparepvec is to be administered only by intralesional injection into cutaneous, subcutaneous and nodal lesions with or without image ultrasound guidance. Talimogene laherparepvec must not be administered into visceral organ metastases.
- The injection site may be pre-treated with a topical anesthetic agent or an injectable local anesthetic; however, a local anesthetic must not be injected directly into the lesion. Please note that the anesthetic should not be mixed together with talimogene laherparepvec in the same syringe. Talimogene laherparepvec does not require any routine premedication.
- Swab the lesion and surrounding areas with alcohol, allow to dry.
- Talimogene laherparepvec is administered by HCP

Figure 4: Timeline of talimogene laherparepvec injection

* Talimogene laherparepvec is administered lower dose for the first course due to possible sero-negative status.

** Biopsy from local disease.

*** Biopsy from distant metastases if available or local disease of non-injection site (optional)

[figure not shown]
Table 3. Talimogene laherparepvec injection volume guideline based on tumor size

Tumor Size (longest dimension)	Maximum Injection Volume
> 5.0 cm	4.0 mL
> 2.5 cm to 5.0 cm	2.0 mL
> 1.5 cm to 2.5 cm	1.0 mL
> 0.5 cm to 1.5 cm	0.5 mL
\leq 0.5 cm	0.1 mL

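### Sections 6.1, 8.2 and 8.3 do not agree on whether fallback local biopsy tissue must be uninjected, and 13.1 does not separate tissue by source

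*Combined protocol and SAP*

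**What the plan says.** Four places in the combined protocol and SAP govern the on-treatment biopsy.

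- Section 8.2 sends two groups to local tissue: "If patient does not have distant metastasis or distant metastasis is not accessible, core biopsy of local lesions will be needed". It sets a best-effort target of tissue from at least 60% of enrolled patients, with no split by tissue source.
- Section 8.3, footnote 8, is equally open on the lesion: "Core biopsy of either distant metastasis or local recurrent lesions before cycle 5 based on patient status".
- Section 6.1, item 3, protects a lesion for one group only: "If patients do not have distant metastases, the lesion of lowest priority for injection should be left uninjected at least until it is biopsied".
- The Figure 4 note in 6.1 reads: "Biopsy from distant metastases if available or local disease of non-injection site (optional".

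The default injection rule, also in 6.1, is extensive: "Lesions should be injected until the maximum volume per day (4.0 mL) has been reached or there are no further injectable lesions". One exception leaves other lesions alone: "If the largest lesion is > 5 cm, only this lesion will be used for injection".

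The biopsy readouts in 8.2 are necrosis, immune-cell markers, cleaved caspase 3, Ki67 and an HSV antigen stain. The analysis plan in 13.1 covers biomarkers in tissue and blood before and after treatment. It does not mention whether the tissue is distant, uninjected local or injected local.

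**The concern.** The lesion-holding rule and the biopsy fallback have different triggers. Patients with distant disease that cannot be sampled fall under the fallback but not under the holding rule. Their local lesions are injected under the ordinary priorities, and one of those lesions may then be biopsied.

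This bears on interpretation. Section 3.0 presents the biopsy of distant disease as a first test in breast cancer of whether systemic immune modulation has antitumour effect, and the fallback tissue is collected under a section on evaluating distant metastases. In an injected lesion, a local viral effect and a systemic immune effect cannot be told apart from necrosis, apoptosis or infiltrate alone. If the source of each specimen is not recorded and used in the analysis, the two kinds of tissue cannot be kept apart when the results are read.

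**Working it through.** **1. The rules side by side**

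| Place | Patients covered | Local lesion to biopsy | Status of the biopsy |
|---|---|---|---|
| 6.1 item 3 | no distant metastases | lowest injection priority, kept uninjected until biopsy | presupposed |
| 6.1 Figure 4 note | distant tissue not available | outside the injection site | optional |
| 8.2 | no distant metastases, or not accessible | any local lesion | described as needed, with a 60% best-effort target |
| 8.3 footnote 8 | according to patient status | any local recurrent lesion | not marked optional |

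The fallback in 8.2 covers patients with no metastases plus patients with inaccessible metastases. Item 3 covers only the first group, so the uncovered group is the patients with inaccessible metastases. The places also differ on tissue source and on whether the biopsy is optional.

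**2. Injections before the biopsy**

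Inputs: the second dose is on day 22 and later doses follow every 2 weeks (6.1; 8.3 footnote 6). The calendar places the biopsy at "Cycle 5 (D64 +/- 5 days".

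Cycle 5 day = 22 + 3 × 14 = 64, which reproduces the calendar. Injections fall on days 1, 22, 36 and 50, so at most four precede the biopsy.

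**3. Can every local lesion have been injected by then?**

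Lesions that can receive their Table 3 maximum at one visit = 4.0 mL / maximum volume per lesion.

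| Longest dimension | Maximum volume | Lesions per visit |
|---|---|---|
| > 2.5 to 5.0 cm | 2.0 mL | 4.0 / 2.0 = 2 |
| > 1.5 to 2.5 cm | 1.0 mL | 4.0 / 1.0 = 4 |
| > 0.5 to 1.5 cm | 0.5 mL | 4.0 / 0.5 = 8 |
| ≤ 0.5 cm | 0.1 mL | 4.0 / 0.1 = 40 |

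A patient with few or small lesions could have all of them injected at a single visit. Entry criterion 5.1.10 can be met with "At least 1 injectable lesion", so some patients may have no second local lesion at all, including some without metastases.

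**4. How many biopsies are affected?**

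The target is 0.60 × 35 = 21 patients, or 0.60 × 36 = 21.6, rounded up to 22.

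Affected biopsies = biopsies taken × share that are local because distant disease is inaccessible × share of those from an injected lesion.

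The documents give neither share. The product could lie anywhere from none to all of the biopsies, so no estimate follows.

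**5. Why the source matters for attribution**

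In the phase 1 study summarised in 4.4.3, 13 of 19 tumour-containing biopsies (68%) showed necrosis, and every necrotic biopsy stained strongly for HSV. Necrosis in injected tumour therefore went with local virus. Section 4.1 also reports an effect up to 6 cm from the injection site, so an uninjected lesion close to an injected one is not certain to be free of direct effect.

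**The case against.** The strongest reply is that this is a wording gap with safeguards around it.

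- **Intent.** The Figure 4 note names an uninjected site, and read with 8.2 it suggests that uninjected tissue was meant. This partly stands. But 8.2 and footnote 8 do not say so, the note makes the biopsy optional, and no rule keeps a lesion available for the uncovered group. The drawing itself is not in the text available for review, so the timing of its biopsy notes could not be checked.
- **Use of the tissue.** A reader might infer that the plan assigns injected fallback tissue to the systemic claim. The documents do not support that. Section 1.3 ties the distant-tissue assessment to distant samples actually obtained, and it also lists injection-site effects as an aim. Injected tissue therefore answers a stated question, which is a reason to identify it and report it separately.
- **Pooling.** A reader might also infer that 13.1 pools all tissue. It does not say so; it is silent on source. The defect is a missing rule.
- **HSV stain.** The planned antigen stain can flag direct viral effect, and in phase 1 non-necrotic tissue very rarely stained. This stands in part. The documented link is with necrosis; for T-cell staining the phase 1 report found no obvious pattern and had no baseline. No analysis rule uses the stain.
- **Existing records.** Section 9.0 requires photographs of local lesions with an injection marker, so part of the injection history is already captured.
- **Upper bound.** Four injections is a maximum. The exception for a largest lesion above 5 cm, and size priority under the 4.0 mL cap, can leave smaller lesions untouched. This stands.

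**Conclusion.** The point holds as an inconsistency on trigger, tissue source and mandatory or optional status, together with an analysis plan that does not distinguish tissue sources. For patients with inaccessible metastases, following 8.2 and the injection rules as written can yield tissue injected up to four times, and a systemic effect cannot be read from it.

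The size is unknown. It is tempting to multiply the phase 1 necrosis rate by an assumed share of injected biopsies: 0.25 × 0.68 = 0.17, or 0.50 × 0.68 = 0.34. The documents do not support those figures as an estimate. The shares are invented, the 68% comes from a 30-patient mixed-tumour study (14 with breast cancer) with different dosing and at most three doses, and the product treats all necrosis as a drug effect.

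The reach is limited to the correlative objective. The primary response endpoint, the two-stage rule, the sample size and the toxicity boundary are unaffected. It is still worth correcting, because the change is cheap and a lesion's injection status may be hard to reconstruct if it is not recorded at biopsy.

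**What to change.** - **Reconcile the text.** Section 6.1 item 3, the Figure 4 note, 8.2 and footnote 8 of 8.3 must agree on which patients trigger local biopsy, what tissue source is intended, and whether the biopsy is required or optional. How lesions are managed is for the sponsor to decide; no injection or biopsy rule is proposed here.
- **Record the source.** For each on-treatment biopsy, record whether it is distant, never-injected local or injected local, the lesion's injection history to that date, and its distance from the nearest injected lesion.
- **Use it in 13.1.** Report the three groups separately, read alongside the HSV antigen stain. Do not base statements about systemic effect on injected tissue. Give distance from injection for never-injected local tissue, in view of the 6 cm figure in 4.1. Injected tissue remains usable for the injection-site aim in 1.3.

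The cost is protocol wording and a few data fields, with no added biopsy. The groups available for the systemic question become smaller, possibly clearly smaller, because one injectable lesion is enough for entry and some patients will have no uninjected local tissue to offer.
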